## ◆ Summary of Protocol

Title	An Open Label, Multicenter, Retrospective, Pivotal Trial to Evaluate the Efficacy of Clinical Decision Support System-mPDia for Neurodegenerative Parkinsonism using MRI images					
Institution	10 hospitals consisting of Gachon University Gil hospital et. al (Gangnam Severance Hospital, Kyung Hee University Hospital, Korea University Guro Hospital, Korea University Ansan Hospital, Seoul St. Mary's Hospital, Seoul Asan Hospital, Hallym University Dongtan Sacred Heart Hospital, Hallym University Pyeongchon Sacred Heart Hospital, CHA Bundang Medical center)					
Investigational Device	Product name: mPDia Item Name: Clinical Decision Support System Manufacturer: Heuron Co.,Ltd					
Purpose	This trial is to check if the diagnosis results of mPDia would meet the success criteria, which is the lower limit of the 95% confidence interval satisfying 88.2% sensitivity and 70% specificity, while using final clinical diagnosis results of medical specialist groups as a golden standard. When the success criteria of mPDia, which is established based on prior reported sensitivity and specificity of neurodegenerative Parkinsonism diagnosis research, is satisfied, it is determined to have efficacy in assisting diagnosis of Parkinsonism.					
Design	Open label, Multicenter, Retrospective, Pivotal clinical trial					
Target case amount	
Total of 221 cases
 
The sensitivity and specificity goal were set as 95% and 86%, respectively, and the lower limit of the 95% confidence interval, which is the success criteria of this study, was calculated as 88.2% and 70%, respectively. The necessary case (image) amount for calculation was 144 people and 56 people. Considering the 10% dropout rate, 159 people for the patient group and 62 people for the normal group, which is 221 people in total, was calculated.
 
  
 Clinical performance target (<math>P_1</math>)	Least clinical performance (= lower limit of 95% confidence interval) (<math>P_0</math>)	N	+10% dropout rate	Total	
  
	Clinical performance target ( $P_1$ )	Least clinical performance (= lower limit of 95% confidence interval) ( $P_0$ )	N	+10% dropout rate	Total
Clinical performance target ( $P_1$ )	Least clinical performance (= lower limit of 95% confidence interval) ( $P_0$ )	N	+10% dropout rate	Total		

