	
 
 Sensitivity: 0.950	Sensitivity: 0.882	144	159		
 
 Specificity: 0.860	Specificity: 0.700	56	62	221	
 
	Sensitivity: 0.950	Sensitivity: 0.882	144	159		Specificity: 0.860	Specificity: 0.700	56	62	221
Sensitivity: 0.950	Sensitivity: 0.882	144	159								
Specificity: 0.860	Specificity: 0.700	56	62	221							
Inclusion Criteria and Exclusion Criteria	
1. Inclusion Criteria
 
Normal group
 
 
1) Adult more than 19 years old
 
2) Person with confirmed 3T nigrosome 1 MRI image
 
3) Person with confirmed normal <math>^{18}\text{F}</math> FP-CIT PET/CT image
 
4) Research participant who visited clinic with parkinsonian symptom as chief complaint that did not correspond to neurodegenerative parkinsonism or healthy participant.
 
 
Patient group
 
 
1) Adult more than 19 years old
 
2) Person with confirmed 3T nigrosome 1 MRI image
 
3) Person with confirmed abnormal <math>^{18}\text{F}</math> FP-CIT PET/CT image
 
4) Person who visited clinic with parkinsonian symptom as chief complaint and was diagnosed as neurodegenerative parkinsonism (multiple system atrophy parkinsonian type, progressive supranuclear palsy).
 
 
2. Exclusion Criteria
 
 
1) Patient with encephalopathy besides parkinsonism.
 
2) Person with anatomic abnormality confirmed by MRI etc.
 
3) Person with other causative disease in advance. (ex: thyroid disease)
 
4) Patient with lesion in basal ganglia such as in Vascular Parkinsonism, Hydrocephalus, Wilson's disease.
 
5) Other cases that the researcher determines to be unsuitable for this clinical trial.
 
 
* Specific reason will be documented in the case report form
										

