Data collecting method	
The following data will be collected retrospectively from person whose past 3T nigrosome 1 MRI image, F FP-CIT PET/CT image, image interpretation, and neurologic exam results are confirmed by medical records, and those whose diagnosis as neurodegenerative parkinsonism is confirmed.
 
Data collecting must be executed following the protocol 10.2 random collection. Only the verified researcher who is registered in this study will have access to medical records. Data collected for this study will be as follows:
 
 
- Demographic information
 
- Environmental factor and medical history/past history
 
- Family history
 
- MDS-UPDRS assessment results
 
- Check Red Flag signs suggestive of PD plus syndrome
 
- Non-motor symptom assessment scale results of Parkinson's disease
 
- REM sleep behavior disorder screening results
 
- Check of any pain
 
- Cognitive function test (K-MMSE, K-MoCA) results
 
- S&E ADL test results
 
- Hoehn & Yahr stage test results
 
- F FP-CIT PET/CT image and interpretation results
 
- Results of neurologic exam and decision of neurodegenerative parkinsonism
 
- Confirmed 3T nigrosome 1 MRI image
 
 
Data used in this study have been collected by the 10 participating institutions from May 1st, 2018 to the starting period of the clinical trial. Data used for the education of the investigational device were collected from November 1st, 2014 to April 30th, 2018 by one institution (Gachon University Gil Hospital), making it mutually independent.

------------------------	--

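### At the training hospital, which is also a test site, the summary separates training from test data by collection date only; independence should be stated and checked per patient

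*Combined protocol and SAP*

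**What the plan says.** All references are to the Summary of Protocol, the only part of the protocol available for this review.

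- **Data collecting method, test data:** "Data used in this study have been collected by the 10 participating institutions from May 1st, 2018" up to the start of the trial.
- **Data collecting method, training data:** these "were collected from November 1st, 2014 to April 30th, 2018 by one institution (Gachon University Gil Hospital), making it mutually independent". No other section is cited in support of the independence.
- **Institution:** the test sites are "10 hospitals consisting of Gachon University Gil hospital et. al". The training hospital is therefore the first-named test site.
- **Inclusion criteria:** both groups need, among other things, a "Person with confirmed 3T nigrosome 1 MRI image". None of the five exclusion criteria mentions earlier use of a person's images in training. The nearest is the discretionary last one, "Other cases that the researcher determines to be unsuitable for this clinical trial".
- **Selection:** "Data collecting must be executed following the protocol 10.2 random collection". The image blinding step refers to section 10.1. Neither section was available for this review.

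**The concern.** Independence is presented as following from the dates and the institution. For nine hospitals that reasoning is sound, since both differ. For the tenth only the date differs. A person scanned there in 2016, used in training, and scanned again in 2019 fits both windows, and nothing in the summary keeps that person out of the test set except a researcher's judgement.

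A device tends to classify people it was trained on better than new people. The summary's efficacy endpoints are sensitivity and specificity, each judged by whether its lower 95% limit reaches a fixed value (88.2% and 70%). No comparator arm exists in which such a bias could cancel, so any overlap would be expected to push both endpoints in the device's favour.

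**Working it through.** **1. Where the gap lies**

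| Sites | Different institution from training | Different date window | What the separation covers |
|---|---|---|---|
| Nine other hospitals | Yes | Yes | Institution and records |
| Training hospital | No | Yes | Records only |

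**2. The plan's own sample sizes**

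Inputs from Target case amount: targets P1 = 0.95 and 0.86; limits P0 = 0.882 and 0.70. Alpha and power are not given in the summary; I assume two-sided 0.05 and 80%.

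n = {[1.96·√(P0(1−P0)) + 0.8416·√(P1(1−P1))] / (P1−P0)}²

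- Sensitivity: [(0.6323 + 0.1834)/0.068]² = 143.9, so 144.
- Specificity: [(0.8982 + 0.2920)/0.16]² = 55.3, so 56.
- With 10% added: 144 × 1.10 = 158.4, so 159; 56 × 1.10 = 61.6, so 62; total 221.

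These match the plan. The point made here changes no sample size.

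**3. Pass counts**

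The summary does not name the interval method; I assume exact (Clopper-Pearson) 95% limits.

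- Sensitivity: 135/144 has lower limit 88.5% and passes; 134/144 has 87.6% and fails.
- Specificity: 47/56 has lower limit 71.7% and passes; 46/56 has 69.6% and fails.

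**4. Effect of overlap**

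The documents give neither site shares nor repeat counts. I assume equal shares, so the training hospital supplies 144/10, about 14 patients, and 56/10, about 6 normals. Let k of these be repeats, and let true accuracy in new people equal the limit. If repeats are always correct (an upper bound), the false-pass probability is:

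- sensitivity: P(X ≥ 135−k), X ~ Bin(144−k, 0.882);
- specificity: P(X ≥ 47−k), X ~ Bin(56−k, 0.70).

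If the error rate among repeats is only halved, their accuracy is 94.1% and 85%, and their count is convolved with the rest.

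| Overlap, all cases | k (patients / normals) | Sensitivity: always correct | Sensitivity: error halved | Specificity: always correct | Specificity: error halved |
|---|---|---|---|---|---|
| None | 0 / 0 | 2.0% | 2.0% | 1.3% | 1.3% |
| About 2% | 3 / 1 | 2.4% | 2.2% | 1.6% | 1.5% |
| About 5% | 7 / 3 | 3.2% | 2.5% | 2.3% | 1.8% |
| About 10% | 14 / 6 | 4.9% | 3.2% | 4.0% | 2.4% |

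The last row is the ceiling at equal shares: every case from the training hospital is a repeat.

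**5. Shift in expected performance (always correct)**

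Shift = overlap × (1−P0). At 2%: 0.02 × 0.118 = 0.24 points for sensitivity and 0.02 × 0.30 = 0.60 points for specificity.

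**6. Both endpoints together**

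Take the two endpoints as independent and require both to pass. At about 2% always-correct overlap:

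- sensitivity at its limit, specificity at its 86% target: false pass goes from 1.5% to 1.9%;
- specificity at its limit, sensitivity at its 95% target: from 1.1% to 1.3%.

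**7. Sensitivity to the interval method**

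With Wald limits the pass counts are 134/144 and 46/56. About 2% always-correct overlap then moves false pass from 4.0% to 4.8% and from 2.9% to 3.4%. Wilson limits give 135/144 and 46/56. The baseline depends on the method, but the increment from overlap stays below one percentage point.

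**The case against.** **The detailed sections may already cover this.** A patient-level selection rule would normally sit in section 10.1 or 10.2. This stands: a reader might infer that the full protocol lacks such a rule, and the available text cannot show that. The reason the summary gives for independence is still insufficient for the training hospital, so a cross-reference is needed in any case.

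**The route is narrow.** Eligible people are those whose MRI "FP-CIT PET/CT image, image interpretation, and neurologic exam results are confirmed by medical records" alongside the other listed items, and the natural reading places all of these in the later window. A training patient would then need a second nigrosome MRI, a second PET/CT and a new examination at the same hospital, and would have to be drawn in the random collection. This largely stands. A reader might infer that the test set is contaminated; nothing in the documents shows that anyone took this route. But the summary does not say whether collection means scan date or extraction date, and a rare event is not an excluded one.

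**The sentence is about data, not people.** The records do come from disjoint windows, and the sentence is true in that sense. For a test of a trained device, however, the independence that matters is that of the people tested.

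**The effect is too small to matter.** A two-sided 95% interval leaves a nominal 2.5% on the passing side. With exact limits and 2% overlap, false pass stays below that even if repeats are always correct. This stands as a limit on size. A reader might fix on 4.9% and 4.0%, but these require every case from the training hospital to be an always-correct repeat, which nothing in the documents suggests.

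**Conclusion.** The point holds as a cheap improvement, not as a demonstrated bias. The summary's independence claim is established for nine sites and, at patient level, not for the training hospital. Any overlap would be expected to favour the device on both endpoints. At 2% overlap with repeats always correct, expected sensitivity rises by about 0.2 points and specificity by 0.6, and false pass goes from 2.0% to 2.4% and from 1.3% to 1.6%. These figures assume exact limits, equal site shares, 144 and 56 evaluable cases, and true accuracy at the limits; the overlap fraction itself is an assumption. Confidence is medium, because sections 10.1 and 10.2 could not be read.

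**What to change.** If section 10.1 or 10.2 already excludes people used in training, cite that rule next to the independence statement. The cost is one cross-reference.

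If not:

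1. Add an exclusion criterion: any person with an image in the mPDia training or tuning set.
2. Apply it by matching patient identifiers at the training hospital before random collection. It cannot wait until the images have been blinded, because non-image information is removed at that step.
3. Restate independence as patient-level, and report how many people the match removed.

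The cost is one identifier match at one hospital. Because it precedes random collection, excluded people are replaced from the remaining pool, and the planned numbers ("Considering the 10% dropout rate, 159 people for the patient group and 62 people for the normal group") need not change.

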
Study Method
	<pre> graph LR     A[Retrospective random data collection] --> B[Exclusion Criteria]     B --> C[Suitable]     B --> D[Unsuitable]     C --> E[Blinding (Blinding coordinator of each institution)]     D --> F[Preparation of Golden Standard]     E --> G[Independent execution]     E --> H[Interpretation of neurodegenerative parkinsonism by software (normal/abnormal)]     G --> I[Independent interpreter of each institution]     H --> I     I --> J["(Independent statistician)"]     J --> K[Calculation of sensitivity/specificity of investigational device]   </pre> 
1. Image blinding
 
The blinding coordinator will select 3T nigrosome 1 MRI image from data collected by the 10.1 data collection method and blind all non-image information such as the belonging group or demographic information.
 
2. Interpretation using mPDia
 
The blinded image will be delivered to an independent interpreter and the interpreter will sequentially upload the image on mPDia according to the image number, check the result, and save it. The saved results will be printed to be used as source document. The results should be blinded, so the saved and printed results should have separate passwords or be in a locked space so that researchers other than the independent interpreter have no access. The independent interpreter should be a neurologist or radiologist of each site who is not participating in this study and should be educated of mPDia usage for this study. Interpretation using mPDia should be performed independently from golden standard creation, and an independent statistician of the sponsor collects the mPDia interpretation data.
 
3. Golden Standard
 
[name], a neurologist of Gachon University Gil Hospital, [name], a radiologist of Gachon University Gil Hospital, will check the collected medical records, provide final diagnosis to the registered candidate based on protocol 10.5.1 neurodegenerative parkinsonism diagnosis checklist and check on the following

---------------------	--

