	
neurodegenerative parkinsonism classification chart. Cases corresponding to Parkinson's disease or atypical Parkinsonian syndromes are defined as neurodegenerative parkinsonism diagnosis. Besides such cases, it is defined not to be neurodegenerative parkinsonism. Only when corresponding to neurodegenerative parkinsonism can the positive response of mPDia regarding neurodegenerative parkinsonism be confirmed. The following diagnosis results will be used as a golden standard in this study.
 
1) Positive in neurodegenerative parkinsonism 2) Negative in neurodegenerative parkinsonism
 
When opinions of two specialists are different, the two will discuss to reach a consensus and record it on the final diagnosis result. All discussed contents will be documented on the Note to file. Golden standard creation must be performed independently from mPDia interpretation, and the golden standard data will be collected by an independent statistician of the sponsor.
 
4. Independent statistician
 
The independent statistician of this study will be Doctor [name] of Heuron Co.,Inc. Without participating in this study, the independent statistician will collect mPDia interpretation results and golden standard and save them in a separate hardware which only the independent statistician can have access to. The independent statistician cannot open the interpretation results or golden standard before statistical analysis is finished.

Study Period	12 months from IRB approval date
Endpoint	
1. Efficacy endpoint Sensitivity and specificity of mPDia for diagnosis of neurodegenerative parkinsonism using final diagnosis results of the specialist group as a golden standard
 
2. Efficacy endpoint assessment method

With the following calculation methods, sensitivity and specificity are calculated, and the 95% confidence interval is provided and evaluated to assess whether the lower limit of the 95% confidence interval reaches 88.2% sensitivity and 70% specificity, which is the success criteria of mPDia, in comparison to the golden standard, which is the final clinical diagnosis result of the specialist group for diagnosis of neurodegenerative parkinsonism.

< Sensitivity and specificity calculation method >

Results	Golden standard			True positive + False positive
	Positive	Negative	Total	
Investigational Device (mPDia)	Positive	True positive (TP)	False positive (FP)	True positive + False positive

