	Negative	False negative (FN)	True negative (TN)	False negative + True negative
	Total	True positive + False negative	False positive + True negative	N

- Sensitivity:  $100 \times \text{True positive (TP)} / [\text{True positive (TP)} + \text{False negative (FN)}] (\%)$
- Specificity:  $100 \times \text{True negative (TN)} / [\text{False positive (FP)} + \text{True negative (TN)}] (\%)$

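### Does the rule on when the statistician may open the two data files make the analysis impossible?

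*Combined protocol and SAP*

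**What the plan says.** Everything on this point is in the Summary of Protocol, under Study Method and Endpoint.

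- **Device readings (Study Method, item 2).** An independent interpreter at each site runs the blinded images through mPDia. "The saved results will be printed to be used as source document", and other researchers are kept away from the results. Then "an independent statistician of the sponsor collects the mPDia interpretation data".
- **Golden standard (item 3).** Two specialists, a neurologist and a radiologist, settle each final diagnosis, by documented consensus where they differ. This must be done independently of the mPDia reading, and "the golden standard data will be collected by an independent statistician of the sponsor".
- **Custody (item 4).** The statistician is to collect both sets and "save them in a separate hardware which only the independent statistician can have access to".
- **Access (item 4).** "The independent statistician cannot open the interpretation results or golden standard before statistical analysis is finished".
- **Analysis (Endpoint).** Sensitivity and specificity are calculated from the 2×2 table of mPDia result against golden standard. The lower limits of the 95% confidence intervals are compared with 88.2% and 70%. In the flow chart the statistician stands directly before the step "Calculation of sensitivity/specificity of investigational device".

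**The concern.** The access rule appears to forbid the work it is meant to protect. The analysis is a cross-classification of two files. The only person with access to the stored copies may open neither until the analysis is finished, and it cannot be finished, or started, with both closed. The summary names no other analyst and no lock or transfer after which opening is allowed.

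The wider worry is control of the comparison. The statistician is employed by the device manufacturer. The device readings and the diagnoses must be independent, but no order is set between them, so one file could be complete while the other is still being made. Two steps involve judgement: consensus after disagreement, and exclusion of cases that the researcher considers unsuitable. If the only rule on access has to be set aside to do the work, a reader cannot tell from the summary whether both files were final before they were compared.

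**Working it through.** **1. Is the literal reading circular?** Take what each quantity needs:

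| Quantity | mPDia result needed | Golden standard needed |
|---|---|---|
| TP, FP, FN, TN | yes | yes |
| Sensitivity = TP / (TP + FN) | yes | yes |
| Specificity = TN / (FP + TN) | yes | yes |

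The denominator of sensitivity, "True positive + False negative", is simply the count of golden-standard positives, but its numerator needs both results for the same case. With both files closed, 0 of 4 cells and 0 of 2 endpoints can be calculated. So the sentence cannot be followed literally.

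**2. Is the literal reading the only one?** No. The summary is written in non-idiomatic English. Under the data collecting method, for instance, it speaks of the device's education where training is evidently meant. In that style, *open* can stand for *disclose*. The statistician may then work on the files but reveals nothing until the analysis is done. That rule can be kept. The text does not settle which meaning was intended.

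**3. What would be done under each reading?**

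- Literal: the rule has to give way at the moment of analysis. The natural moment is when both files are complete, since a sensitivity or specificity over all cases needs every pair.
- Disclosure: the files are merged when complete and the results released afterwards.

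The table, the two proportions and the comparison with the limits are the same.

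**4. Does any planned figure depend on the rule?** The sample size can be reproduced without it. For one proportion,

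n = [(z₁√(p₀(1−p₀)) + z₂√(p₁(1−p₁))) / (p₁−p₀)]²

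with z₁ = 1.960 (two-sided 5%, implied by the 95% interval) and z₂ = 0.842 (80% power, which is assumed because the summary states none):

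- Sensitivity, p₀ = 0.882 and p₁ = 0.95: n = 143.90, rounded up to 144 (plan: 144).
- Specificity, p₀ = 0.70 and p₁ = 0.86: n = 55.34, rounded up to 56 (plan: 56).
- Dropout as the plan applies it: 144 × 1.10 = 158.4, giving 159; 56 × 1.10 = 61.6, giving 62; 159 + 62 = 221 (plan: 221).

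The access rule enters none of these figures, nor the definition of either endpoint.

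**5. How could early opening reach the result?** The statistician makes neither the readings nor the diagnoses. To change a result, case-level information would have to pass from the statistician to the interpreters, to the two specialists or to those who exclude cases. The first two routes breach the independence that items 2 and 3 already require. For exclusions, the plan calls for specific reasons in the case report form, and the flow chart places the exclusion check ahead of blinding and reading. Device output also exists as printed source documents, and consensus discussions are recorded in a note to file.

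**The case for a change.** The best case for a change is that both readings lead to the same correction. Read literally, the rule forbids the analysis. Read as a rule on disclosure, it can be kept, but the summary then says nothing about when the statistician may look. The independence requirements keep interpreters and specialists from seeing each other's results; they do not date the moment of comparison. With a statistician from the manufacturer and no set order between the two files, a dated lock would cost little and would let a reader verify the sequence.

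Part of this stands. The sentence is badly worded, and the summary states no release point for opening the files. A lock date would make the record easier to audit.

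The step from there to a needed change does not stand, for three reasons. The summary refers to procedures in sections 10.1, 10.2 and 10.5.1, which were not available, so a release point missing from the summary is not shown to be missing from the protocol. The flow chart adds little: as extracted it sends unsuitable cases to the preparation of the golden standard, so one arrow in it cannot carry weight. And the contact that would make early opening harmful is already excluded by the independence rules. A lock would document the sequence better, but it would not change what the interpreters and specialists are allowed to know.

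**Conclusion.** No change follows. The sentence is a wording slip: circular if taken literally, workable if it means disclosure, and in either case resolved in the same way by anyone doing the analysis. Its size is nil for the planned figures. The 144, 56 and 221 cases, the 88.2% and 70% limits and both endpoint definitions are unaffected, and no effect on sensitivity or specificity is shown.

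This rests on three assumptions: that the files are merged only when both are complete, that the independence required of the readings and the diagnoses is observed, and that exclusions are decided without knowledge of the comparison. Nothing in the documents suggests otherwise. Clearer wording would be a courtesy to readers; the validity of the trial does not depend on it.
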